#### **13.2 Winship Cancer Institute Data Safety Monitoring Committee:**

The study will also be followed by the Winship Cancer Institute Data Safety Monitoring Committee to allow for local review and confirmation of proper study execution and safety measures.

**13.2.1** Patient safety, study efficacy and compliance will be reviewed at the Neuro-oncology Working Group meeting. The Data and Safety Monitoring Committee (DSMC) of the

Winship Cancer Institute will also oversee the conduct of this study (annually or semi-annually – depending on the risk level assigned to the protocol by the Winship Cancer Institute Clinical and Translational Research Committee). The DSMC will review pertinent aspects of study conduct including patient safety, compliance with protocol, data collection and efficacy. The committee will review the charts of 10% of patients enrolled to the study and two of the first 5 patients entered to the study. The Committee reserves the right to conduct additional audits if necessary. The clinical Principal Investigator (PI) at each site or his designee is responsible for notifying the DSMC about the accrual of patients when the first 5 have been entered to the study. The PI or designee will also notify the DSMC of study status within 2 months before the next scheduled review is due.

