    - Each site Principal Investigators (PI) are responsible for review and assessment of all adverse events at their site as specified in the protocol. AEs, SAEs (initial and follow ups), and UPs will be reported to the each site IRB as per protocol requirements

including reporting SAEs and UPs within 24 hours of the participating site becoming aware of the event.

- Johns Hopkins and University of Miami sites are also responsible for the following:
  - Report events, as applicable, to their IRB.
  - Submit all acknowledgements of reports submitted promptly to their IRB to the Winship multisite coordinator or Emory PIs.
  - Resolve all queries related to the SAE report in a timely manner.
  - Maintain copies of each event reported in the subject's study records.
  - Enter AEs into Oncore® in a timely manner.
  - Enter SAEs and UPs into Oncore® or equivalent (depending on the institution) in the SAE category, in a timely manner.
- Winship multisite coordinator will inform all three sites of adverse events that require expedited reporting to local IRBs.
- Emory Lead investigator will review SAE data summary reports on a regular basis, at least annually
- Emory Lead investigator will submit SAE data summary reports to the Data Safety Monitoring Committee for review as per their guidelines.

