**14.4 Adverse event stopping rule:** Safety assessments will be performed throughout treatment, at two week intervals during RT and prior to each odd number adjuvant TMZ cycle following completion of RT. Toxicity will be carefully assessed using CTCAE v4.03 criteria, and the rate of radiation necrosis development will be determined. While we expect this regimen to be tolerated based on the previous experience reported by Tsien et al. [9], we will still employ an interim safety analysis with a special stopping rule if neurotoxicity is greater than expected. Because the expected incidence of late grade 3+ neurotoxicity with standard-of-care chemoradiation is ~5%, or 2 of 30 patients in our planned cohort, we will employ the following interim analysis and stopping rule after 10 subjects have completed treatment and have been followed for 6 months after completion of chemoradiation: if more than 2 subjects (out of 10) develop CTCAE v4.03 grade III or greater neurotoxicity (> 20% incidence) judged to be at least possibly due to RT by 6 months from completion of RT/TMZ, study accrual will halt and await assessment of toxicities by the DSMC to review attribution of toxicities before a decision will be made about either permanent closure or re-opening with continuation/completion of study accrual.

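### The only accrual-halting rule counts neurotoxicity alone and weighs a death like a grade 3 event, so one or two RT-attributed deaths among the first 10 cause neither a halt nor an event-triggered DSMC review

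*Combined protocol and SAP*

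**What the plan says.** Section 14.4 sets one interim look, "after 10 subjects have completed treatment and have been followed for 6 months after completion of chemoradiation". The rule acts "if more than 2 subjects (out of 10) develop CTCAE v4.03 grade III or greater neurotoxicity" that is "judged to be at least possibly due to RT by 6 months from completion of RT/TMZ". If three or more of the 10 have such an event, "study accrual will halt and await assessment of toxicities by the DSMC". The reference point is that the "expected incidence of late grade 3+ neurotoxicity with standard-of-care chemoradiation is ~5%, or 2 of 30 patients".

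Section 14.8 refers only to Section 14.4 for toxicity stopping, and says that about 20 patients will have begun therapy by the time of the look. Section 14.1.2 covers grade 3+ toxicity of every kind. Its threshold is more than 6 of 30, and its consequence is review by the study team, with no halt and no DSMC.

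On the DSMC, Section 13.2.1 says that it "will also oversee the conduct of this study (annually or semi-annually", depending on the assigned risk level. Section 13.2.2.5 adds: "Emory Lead investigator will review SAE data summary reports on a regular basis, at least annually", and "Emory Lead investigator will submit SAE data summary reports to the Data Safety Monitoring Committee for review as per their guidelines".

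**The concern.** Every patient is planned for the escalated dose, and safety is a primary objective (Section 2.1.2). The outcome that a monitoring committee would most want to hear of at once is a death attributed to that dose. Under Section 14.4 such a death counts as one of the three events needed, the same as a reversible grade 3 event. If it is classed as non-neurological, it counts as none. After the single look at 10 patients, no halting rule remains.

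At stake is whether enrolment at three sites could continue after one or two such deaths without the DSMC, which Section 14.4 makes the reviewer before accrual may resume, having been asked.

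**Working it through.** **Inputs.** Halting count of 3 of 10, attribution, 6-month window and ~5% reference rate: Section 14.4. About 20 started at the look: Section 14.8. Accrual of 30 patients in 1.5 years, or 2–3 a month: Section 14.3. One-year control-arm OS of about 66%: Section 14.3.1. The documents give no fatal toxicity rate for RT, so the fatal rates below are assumptions shown over a range.

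**1. The plan's own figures.** 2/10 = 20%, so more than 2 means above 20%, and the first halting count is 3/10 = 30%. The reference rate gives 5% × 30 = 1.5, rounded up to 2 (2/30 = 6.7%). These reproduce.

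**2. What leaves accrual open.** Let a, b and c be the numbers of patients whose worst attributed neurotoxicity is grade 3, 4 and 5. Accrual halts only if a + b + c ≥ 3. Ten combinations have a total of 2 or less, and they include c = 1 and c = 2. One or two fatal neurotoxicities therefore halt accrual only if other patients bring the total to 3. A non-neurological grade 5 event adds 0, however many there are.

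**3. Chance of a halt, all grade 3+ neurotoxicity together.** With X ~ Binomial(10, p), P(halt) = 1 − Σ(k = 0 to 2) C(10,k) pᵏ(1−p)¹⁰⁻ᵏ.

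| True grade 3+ rate | P(halt) |
|---|---|
| 5% | 1.2% |
| 10% | 7.0% |
| 20% | 32.2% |
| 30% | 61.7% |
| 40% | 83.3% |

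**4. Deaths as the only qualifying events.** At fatal rate q, P(1 or 2 deaths) = P(X ≥ 1) − P(X ≥ 3). For q = 5%: 0.4013 − 0.0115 = 0.3898.

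| Assumed fatal rate | P(at least 1 death in 10) | P(1 or 2, no halt) | P(no halt, given at least 1) |
|---|---|---|---|
| 1% | 9.6% | 9.6% | 99.9% |
| 2% | 18.3% | 18.2% | 99.5% |
| 5% | 40.1% | 39.0% | 97.1% |
| 10% | 65.1% | 58.1% | 89.2% |

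**5. Timing.** The look falls at about 10/r + 42/30.4 + 6 months for accrual of r per month, counting 42 days of chemoradiation. At r = 30/18 this is 13.4 months, with about 22 enrolled. At r = 2 it is 12.4 months, with about 25. At r = 3 it is 10.7 months, with all 30. The plan's figure of about 20 is at the favourable end.

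**6. Other routes for a death, side by side.**
- Site IRB: Section 13.2.2.5 requires SAE reports within 24 hours; Section 12.2 forwards only SAEs judged reportable. The two do not agree.
- Lead investigators: notified (Section 12.2); their review of SAE summaries is at least annual (Section 13.2.2.5).
- Working group: monthly review of toxicities, with extra sessions up to weekly (Section 13.2.2.3), plus monthly cross-site teleconferences (Section 13.3).
- DSMC: SAE summaries under its own guidelines (Section 13.2.2.5) and scheduled annual or semi-annual oversight (Section 13.2.1).

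No section ties any of these to an accrual decision or an unscheduled DSMC review.

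**7. The denominator.** The 10 are subjects who completed treatment and were followed for 6 months. The text does not say whether a patient who dies earlier is one of them.

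**8. Burden of event-triggered review.** P(at least one review in 30) = 1 − (1−q)³⁰, where q is the chance that a patient has a death called at least possibly RT-related. For q = 1%, 3.4% and 5% this is 26%, 65% and 79%. The 3.4% is (1 − 0.66) × 1/10, assuming that one in ten first-year deaths is so attributed.

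**The case against.** A reader might infer that the rule ignores severity and that an RT-attributed death would receive no committee review. The documents do not support that. The rule has a grade III floor; what it lacks is a distinction within grades 3 to 5. A death is an SAE (Section 12.1.2) and reaches the bodies listed in step 6, including a scheduled DSMC review of patient safety.

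A reader might also infer from step 4 that the rule has almost no chance of acting. That calculation leaves out non-fatal events, which count toward the three; step 3 shows 32% at a 20% total rate and 62% at 30%. The higher fatal rates are also hard to anchor. The plan's ~5% is for all late grade 3+ neurotoxicity under standard chemoradiation, and Section 1.0 cites a dose-escalation report with no late grade III or greater CNS toxicity up to 75 Gy, the highest dose prescribed here. The 1% and 2% rows deserve at least as much attention as the others.

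Third, the DSMC's guidelines and the IRBs' requirements are not in the documents and may already call for prompt review of a treatment-related death. That cannot be settled here.

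Finally, attribution as possible is broad under Section 12.3.3, so a death-based trigger could act often in this disease.

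All four points stand and limit the claim. None supplies a stated link from an RT-attributed death to an accrual decision or an unscheduled DSMC review.

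**Conclusion.** The gap is real but narrow. As written, one or two RT-attributed deaths among the first 10, or any number of RT-attributed non-neurological deaths, cause no accrual halt and no event-triggered DSMC review. This follows from the text and needs no assumed rate.

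Its size does depend on assumptions. With deaths as the only qualifying events and independent patients, the chance of one or two deaths without a halt is 10% to 18% at fatal rates of 1% to 2%, and 39% to 58% at 5% to 10%. Concurrent grade 3 or 4 neurotoxicity would reduce the chance that accrual continues.

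The plan should be changed, because patient safety is a primary objective and the committee and reporting channel already exist. The documents do not support a claim that deaths go unreviewed, and this point does not establish which halting rule would be right.

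**What to change.** Amend Sections 14.4 and 13.2.2.5 so that any grade 5 event, of any organ class, judged at least possibly due to the dose-escalated RT goes from the site to the lead site and on to the existing DSMC on the existing 24-hour SAE timeline. The DSMC then holds an unscheduled review and decides whether accrual continues. Any specific halting rule is for the sponsor and the DSMC to set.

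State in Section 14.4 that subjects who die before completing treatment or 6 months of follow-up count among the 10.

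Reconcile two pairs of passages: Section 12.2 (only SAEs judged reportable) with Section 13.2.2.5 (24 hours), and the neurotoxicity-only scope of Section 14.4 with the all-toxicity scope of Section 14.1.2.

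The cost is protocol wording and more unscheduled DSMC reviews. If 3.4% to 5% of patients have a death called possibly related, 65% to 79% of trials of this size would see at least one. Leaving accrual to the DSMC's judgement, with no automatic halt, keeps that burden manageable.

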**Accrual**

Rate: 1 pts/month/site

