### **3.4 Patient Selection - Exclusion Criteria:**

- 3.4.1** Patients with pacemakers, aneurysm clips, neurostimulators, cochlear implants, metal in ocular structures, history of being a steel worker, or other incompatible implants which makes MRI safety an issue are excluded.
- 3.4.2** Patients that have any significant medical illnesses that in the investigator's opinion cannot be adequately controlled with appropriate therapy or would compromise the patient's ability to tolerate this therapy are excluded.
- 3.4.3** Patients with a history of any other invasive cancer (except non-melanoma skin cancer and excluding carcinoma in-situ), unless in complete remission and off of all therapy for that disease for  $\geq 3$  years, are ineligible.
- 3.4.4** Patients with an active infection or serious intercurrent medical illness are ineligible.
- 3.4.5** Patients receiving any other investigational agents are excluded.
- 3.4.6** Patients who have received prior cytotoxic, non-cytotoxic or experimental drug therapies for brain tumor are excluded.
- 3.4.7** Patients with a history of prior cranial radiation are ineligible.
- 3.4.8** Patients may not be enrolled on any other therapeutic trial for which they are receiving an anti-tumor therapy.
- 3.4.9** Patients with GBMs located in the following anatomical regions known to have magnetic susceptibility or poor signal will be excluded: mesial temporal lobe, orbitofrontal cortex, prefrontal cortex, medial frontal gyrus, brainstem, and cerebellum.
- 3.4.10** The maximum radiation target volume for 75 Gy is 65 cc (per NRG Oncology Guide). Patient may be excluded after the first sMRI scan if the 75 Gy volume is greater than 65 cc [we anticipate that contrast-enhancing tumor volume (residual tumor volume following tumor resection) would be less than 20 cc].

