### 14.3 Exploratory Objectives

14.3.1 To determine whether sMRI-guided, dose-escalated RT increases the overall survival of patients with newly-diagnosed GBMs. Subjects on this study will also be followed for overall survival (OS) which is defined from the time of surgical resection to the time of death. The OS actuarial curve and 1-year OS rate will be assessed and compared to historical controls. The 1-year OS rate of control arm patients on recent trials is approximately 66%

14.3.2 To determine whether sMRI data obtained after initiation of therapy (at 2 weeks after RT/TMZ start and prior to cycle 1 and 5 of adjuvant TMZ) will provide early evidence of GBM progression not seen on standard MRIs. Changes in sMRI parameters over time will be assessed to determine whether they will be able to predict development of recurrence. Global changes in sMRI parameters including to absolute metabolite concentrations or metabolic ratios will be examined to see if these factors may be an early marker of tumor recurrence. In addition, further assessments will be made on a voxel-wise basis to determine whether individual changes may be predictive of ultimate recurrence within particular voxels.

14.3.3 To determine whether performance on neurocognitive and quality-of-life (QOL) assessments in newly-diagnosed GBM patients treated with sMRI-guided, dose-escalated RT differ from historical controls. We will compare performance on neurocognitive and QOL assessments in our 30 subject cohort with performance by historical control cohorts from recent GBM trials (eg. RTOG 0525 and 0825) [45, 46]. Better performance may be attributable to better control of disease while worse performance may imply increased toxicity from the study treatment regimen.

**14.3 Accrual rate and numbers:** The anticipated rate of accrual will be 2-3 patients/month among three sites. This will allow consenting of 30 patients over a period of 1.5 years.

**14.3 Criteria for removal from trial:** All reasons for discontinuation of treatment must be documented.

**14.3.1** Progression of disease will be hard to determine due to pseudoprogression as defined in section 11.3. The final progression free survival will be determined at year 1, which is beyond pseudoprogression possibility.

**14.3.2** Patient may withdraw from study at any time for any reason.

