**14.7 Statistical analysis of neurocognitive function and QOL scores:** Linear mixed effects models will be applied to model the repeatedly measured score from each assessment and/or test over time. We hypothesize that changes in individual and/or composite metabolite levels will be predictive of the temporal changing patterns in the scores on the neurocognitive functional tests and QOL assessments. Changes in individual and multiple metabolite levels

within normal brain surrounding the region of the tumor as well as in tumor-bearing regions of brain will be evaluated with scores on these assessments using logistic regression models.

**14.8 Interim analysis and stopping rule for efficacy/futility:** While there will be stopping rules for toxicity/adverse events (see **Section 14.4**), there will not be stopping rules for efficacy/futility. The primary goal of the study is to determine the feasibility and safety of sMRI-guided, dose-escalated RT and TMZ for newly diagnosed GBM patients. At the time we anticipate performing interim analysis for toxicity assessment in the first 10 patients with adequate follow-up, approximately 20 patients will have already initiated therapy allowing up to 10 patients to avoid enrollment if this treatment regimen is determined to be too toxic.

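### The accrual-halt rule in 14.4, read literally, can leave out patients who stop RT early or die before 6 months, and it waits for full follow-up even after a third event

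*Combined protocol and SAP*

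**What the plan says.** **The rule.** Section 14.4 schedules one interim safety look, "after 10 subjects have completed treatment and have been followed for 6 months after completion of chemoradiation". The event is CTCAE grade 3 or higher neurotoxicity, at least possibly due to RT, arising by 6 months from the end of RT/TMZ. If more than 2 of the 10 have one, "study accrual will halt and await assessment of toxicities by the DSMC to review attribution of toxicities"; closure or re-opening is decided after that. Section 14.8 describes the same look differently: "At the time we anticipate performing interim analysis for toxicity assessment in the first 10 patients with adequate follow-up". Its projection for that date is that "approximately 20 patients will have already initiated therapy allowing up to 10 patients to avoid enrollment".

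**Related safety text.** Section 9.1 foresees that neurological worsening may end RT, and it allows RT to be withheld for RT-attributable CNS toxicity of grade 3 or higher. In 14.1.2 the trigger of more than 6 of 30 leads to study-team review, not to an accrual halt. Section 13.2.2 plans monthly toxicity review at all three sites.

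**Accrual text.** The accrual paragraph of 14.3 says "The anticipated rate of accrual will be 2-3 patients/month among three sites" and then "This will allow consenting of 30 patients over a period of 1.5 years". Section 3.1 gives "Rate: 1 pts/month/site", with total accrual of 30 minimum and 43 maximum. Section 3.4.10 adds that "Patient may be excluded after the first sMRI scan if the 75 Gy volume is greater than 65 cc". Section 8.2 puts chemoradiation at about 42 days.

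**The concern.** Safety is a primary objective, and 14.4 is the only place where a count stops enrolment. Its entry condition (treatment completed, then 6 months of follow-up) selects on what happens after treatment starts. The toxicity the rule is meant to detect can itself end RT or end follow-up. A patient removed in this way is replaced by a later starter, so a qualifying event can be lost and the look moves later.

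The rule is also tied to one date. Nothing in 14.4 says that accrual halts when the third event occurs, and no pause is stated while the 10 mature. Patients can keep starting the same regimen after the boundary has in effect been reached.

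The projection in 14.8 tells the reader how many patients the look can protect, so its basis should be visible.

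**Working it through.** **1. Who is counted.** Three kinds of patient among the first 10 starters:

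| Patient | Meets the 14.4 event definition? | Meets the literal entry condition? |
|---|---|---|
| Completes RT, grade 3+ neurotoxicity, reaches 6 months | Yes | Yes |
| Stops RT early because of grade 3+ neurotoxicity | Yes by grade and attribution; the time window has no anchor, because RT was not completed | No |
| Completes RT, dies of RT-attributed neurotoxicity before 6 months | Yes (grade 5) | No |

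Example: 3 of the first 10 starters have qualifying events, and one of the three stopped RT early. Counted by start, that is 3 of 10 and accrual halts. Counted literally, 2 remain and the 11th starter fills the place. There is no halt unless that patient also has an event.

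If k starters fall outside, the 10th counted patient is starter 10 + k, and the look slips by k / (starts per month). For k = 2 this is 2/1.67 = 1.2 months, or 2/3 = 0.67 months at 3 per month.

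Losses before 6 months need not be rare. Section 14.3 cites a 1-year OS of about 66%. Assuming a constant hazard, which may overstate early deaths, survival over 7.38 months is 0.66^(7.38/12) = 0.77, or about 2 deaths per 10 starters. These are deaths from any cause. The documents do not say how many would carry a qualifying toxicity.

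**2. How long the rule waits.** 42/30.44 + 6 = 1.38 + 6 = 7.38 months after the 10th start.

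**3. Crossing chance for a fixed 10.** P(X ≥ 3), X ~ Binomial(10, p):

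| True rate | 5% | 10% | 20% | 30% | 40% |
|---|---|---|---|---|---|
| Chance | 1.2% | 7.0% | 32% | 62% | 83% |

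The running count never falls unless an attribution is downgraded. It therefore reaches three at some time exactly when the final count is three or more, so acting at the third event leaves these chances unchanged.

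**4. The 14.8 projection.** Constant accrual without a pause: started = 10 + rate × wait, capped at 30; spared = 30 − started.

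Reproducing 14.8: 30/18 = 1.67 per month; 10 + 1.67 × 6 = 20 started, 10 spared. This omits the RT course. With it, 10 + 1.67 × 7.38 = 22.3.

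Started / spared with the RT period included:

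| Rate per month | (a) All accrued start | (b) 30 of 43 start (assumption) | (c) As (a), 2 patients replaced (illustration) |
|---|---|---|---|
| 1.67 (30 in 1.5 years) | 22 / 8 | 19 / 11 | 24 / 6 |
| 2 | 25 / 5 | 20 / 10 | 27 / 3 |
| 2.5 | 28 / 2 | 23 / 7 | 30 / 0 |
| 3 (also 1 per site × 3) | 30 / 0 | 25 / 5 | 30 / 0 |

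Exactly 20 started needs 10/7.38 = 1.36 starts per month. The accrual statements need not conflict: 2–3 per month for 18 months is 36–54, and 43/18 = 2.39 per month. But no consent-to-start ratio is given.

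**The case against.** **The cohort is defined.** Section 14.4 gives the number, treatment status, follow-up, event, attribution and window. Section 14.8 points to 14.4, so its looser phrase most naturally means the same 6 months. This stands. A reader might infer that the interim cohort is undefined; the text does not support that. The difficulty is that the definition, followed as written, can omit the patients who matter most.

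**The 14.8 figures are hedged and reproducible.** This also stands. A reader might infer an arithmetic error, with 25–30 started and 0–5 spared as the true figures. That holds only if 2–3 per month counts treated patients with no loss before treatment. The same paragraph of 14.3 speaks of consenting, and 3.4.10 allows exclusion after the first scan. At that rate 30 patients would start in 10–15 months, not 18.

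**Other oversight exists.** Monthly toxicity review and DSMC oversight mean that an early stopper's event would be seen, and the committee could act. That limits the risk, but neither arrangement carries a numeric halt rule.

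**Acting at the third event is a design preference.** It goes further than repairing the cohort wording, and the cohort repair can be made without it. It is worth adding because it keeps the boundary and uses reviews already planned.

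**Conclusion.** The rule can give a wrong answer if followed literally: qualifying grade 3–5 events in early stoppers, or in patients who die before 6 months, can drop out of the count, and each replacement delays the look. How often this would happen, and how far it would change the chance of a halt, cannot be derived from the documents. It would be too strong to say that fatal events are excluded from the event definition. A fatal RT-attributed neurotoxicity is grade 5 and qualifies; what is unsettled is whether that patient is among the 10.

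The wait of about 7.4 months after the 10th start rests on a 42-day course and on the absence of any stated pause.

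The 14.8 projection is a minor wording point. No sample size or error rate uses it, and 20 to 22 started follows from 30 consented in 1.5 years under constant accrual with every consented patient starting. What is missing is a reconciliation with the 2–3 per month in 14.3 and the per-site rate in 3.1.

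**What to change.** 1. In 14.4 and 14.8, define the interim cohort as the first 10 patients to start dose-escalated RT. Count every qualifying event up to 6 months after the last RT fraction received, including events in early stoppers and in patients who die. That end point gives non-completers a time anchor. List each patient's follow-up time for the DSMC.
2. Keep the boundary of more than 2 of 10. Apply the existing accrual halt and DSMC review when the third qualifying event among those 10 is recorded at the toxicity reviews already planned. The order in 14.4 stays: halt first, then review of attribution, then closure or re-opening.
3. State whether each rate in 3.1 and 14.3 counts consented or treated patients. Restate 14.8 as a range that includes the RT period and shows the assumed consent-to-start ratio.

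None of this changes when an individual patient's RT is withheld or resumed.

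**Cost.** Protocol wording only. For the fixed cohort, item 2 leaves the crossing chance unchanged unless an attribution is downgraded. Compared with the literal 14.4 cohort, item 1 may change which patients count, and that effect cannot be derived. A pause may come earlier, on incomplete follow-up of the others or on an attribution that the DSMC reverses; 14.4 already allows re-opening. Patients who die early without an event stay among the 10 with shorter exposure, which is why the follow-up listing is needed.
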